7.1 Critical Baseline Assessments

Efficacy assessments conducted at baseline are described in Section 7.2.2, and tumor tissue [REDACTED] assessments are described in Section 7.4.2. Safety assessments conducted at baseline and during treatment are described in Section 7.3. Cardiovascular medical history/risk factors will be assessed at baseline.

7.1.1 Baseline Confirmation of BRAF V600 Mutation-positive Melanoma

Subjects with histologically confirmed unresectable or metastatic acral lentiginous or cutaneous melanoma that is either Stage IIIC (unresectable) or Stage IV will be screened for eligibility after signing the informed consent form. Subjects will be screened prior to treatment to determine whether their tumor sample has a V600 mutation, indicating their eligibility for the study. Formalin fixed paraffin embedded (FFPE) specimens reflective of the metastatic disease setting is preferred for the mutation testing. Tumor mutation status will be determined in a Novartis designated central lab. Only if clinical outcome data warrants, a companion diagnostic assay may need to be developed for regulatory submission and approval. Additional BRAF mutation testing may be conducted on the screening tissue to support the development of the companion diagnostic assay.

Further details on tissue requirement for BRAF mutation will be provided in the SPM.

7.1.2 Baseline Documentation of Target and Non-target Lesions

All baseline lesion assessments, including brain MRI/CT to rule out brain metastases, must be performed within 4 weeks prior to enrolment.

- Lymph nodes that have a short axis of < 10 mm are considered non-pathological and should not be recorded or followed.
- Pathological lymph nodes with a short axis of < 15 mm but \geq 10 mm are considered non-measurable.
- Pathological lymph nodes with a short axis of \geq 15 mm are considered measurable and can be selected as target lesions. Lymph nodes should not be selected as target lesions when other suitable target lesions are available.
- Measurable lesions up to a maximum of 2 lesions per organ and 5 lesions in total, representative of all involved organs, should be identified as target lesions, and recorded and measured at baseline. These lesions should be selected on the basis of their size (i.e., lesions with the longest diameter) and their suitability for accurate repeated measurements (i.e., either by imaging techniques or clinically).

Note: Cystic lesions thought to represent cystic metastases should not be selected as target lesions when other suitable target lesions are available.

Note: Measurable lesions that have been previously irradiated and have not been shown to be progressing following irradiation should not be considered as target lesions.

- Lytic bone lesions or mixed lytic-blastic lesions, with identifiable soft tissue components, that can be evaluated by CT or MRI can be considered measurable. Bone scans,

fluorodeoxyglucose positron emission tomography (FDG-PET) scans or X-rays are not considered adequate imaging techniques to measure bone lesions.

- All other lesions (or sites of disease) should be identified as non-target and should also be recorded at baseline. Non-target lesions will be grouped by organ. Measurements of these lesions are not required, but the presence or absence of each should be noted throughout follow-up.

7.2 Efficacy

7.2.1 Efficacy Endpoints

7.2.1.1 Primary Efficacy Endpoint

The primary endpoint for this study is objective response rate of dabrafenib in combination with trametinib in subjects with BRAF V600 mutation-positive, unresectable or metastatic acral lentiginous or cutaneous melanoma (ALM). Objective response rate is defined as the percentage of subjects with evidence of confirmed complete response (CR) or partial response (PR) as per RECIST v1.1 [Eisenhauer EA 2009].

7.2.1.2 Secondary Efficacy Endpoints

The secondary efficacy endpoints of this study are:

- Duration of response, defined as the time from first documented evidence of CR or PR until the earliest date of documented radiological progression or death due to any cause among subjects who achieve a confirmed response (i.e. confirmed CR or PR)
- PFS, defined as the time from first dose of study treatment until the first date of either objective disease progression or death due to any cause.
- OS, defined as the interval between the treatment start date and the date of death due to any cause.

7.2.2 Efficacy Assessments

Disease progression and response evaluations will be determined according to the definitions established in RECIST, version 1.1 [Eisenhauer EA 2009].

Refer to the Time and Events Table (Table 20) for the schedule of efficacy assessments.

Assessments must be performed on a calendar schedule and should not be affected by dose interruptions/delays. For post baseline assessments, a window of ± 7 days is permitted to allow for flexible scheduling.

- The following scans/assessments are required at baseline: contrast CT (preferred method) of chest/abdomen/pelvis or MRI of abdomen/pelvis and any area of known disease, skin lesion photography, and clinical disease assessment for palpable lesions. Exception: If a chest CT cannot be performed, chest X-ray can be used only to document **the absence of disease** (no tumor lesions) or the **presence of new lesions**. If lesions are detected at baseline by chest X-ray, chest CT must be done to properly document these lesions at baseline and in follow-up tumor assessments. At each post-baseline assessment, evaluations of the sites of disease identified by these scans are required.

- A baseline brain scan is required for all subjects. For subjects without CNS disease at baseline, subsequent brain scans should only be performed as clinically indicated (e.g. symptoms suggestive of CNS progression). For subjects with CNS disease at baseline, a brain scan is required every 8 weeks or as clinically indicated. In addition, in order to confirm a CR in a subject with brain disease at baseline, a brain scan must be performed 1 week prior to the 1st set of images showing CR to 4 weeks after the next protocol specified assessment.
- If clinically indicated, a contrast enhanced CT or MRI scan of affected bone areas will be required at baseline. Bone lesions, if present as non-target lesions, will continue to be followed consistently throughout the study until disease progression, death, or withdrawal of consent.

Confirmation of CR and PR are required per protocol. Confirmation assessments must be performed no less than four weeks after the criteria for response have initially been met and may be performed at the next protocol scheduled assessment. If a confirmation assessment is performed prior to the next protocol schedule assessment, the next protocol scheduled evaluation is still required (e.g., evaluations must occur at each protocol scheduled time point regardless of unscheduled assessments).

Scans will be assessed by investigators and will be collected and stored. Details related to disease assessment acquisition and image transfer to be applied to baseline and all subsequent imaging will be provided in the SPM.

7.2.2.1 Assessment Guidelines

Please note the following:

- The same diagnostic method, including use of contrast when applicable, must be used throughout the study to evaluate lesions. Contrast agents must be used in accordance with the Image Acquisition Guidelines.
- All measurements should be taken and recorded in millimeters (mm), using a ruler or calipers.
- Ultrasound is not a suitable modality of disease assessment. If new lesions are identified by ultrasound, confirmation by CT or MRI is required.
- Fluorodeoxyglucose-positron emission tomography (FDG-PET) is generally not suitable for ongoing assessments of disease. It can, however, be useful in confirming new sites of disease when a positive FDG-PET scan correlates with the new site of disease present on CT/MRI or when a baseline FDG-PET was previously negative for the site of the new lesion. Fluorodeoxyglucose (FDG)-PET may also be used in lieu of a standard bone scan providing coverage allows interrogation of all likely sites of bone disease and FDG-PET is performed at all assessments.
- If positron emission tomography/computed tomography (PET/CT) is performed then the CT component can only be used for standard response assessments if performed to diagnostic quality, which includes the required anatomical coverage and prescribed use of contrast. The method of assessment should be noted as CT in the eCRF.

Clinical Examination: Clinically detected lesions will only be considered measurable when they are superficial (e.g., skin nodules). In the case of skin lesions, documentation by color photography, including a ruler/calipers to measure the size of the lesion, is required [Eisenhauer EA 2009]. See SPM for details.

CT and MRI: Contrast enhanced CT with 5 mm contiguous slices is recommended. Minimum size of a measurable baseline lesion should be twice the slice thickness, with a minimum lesion size of 10 mm when the slice thickness is 5 mm. Magnetic resonance imaging (MRI) is acceptable, but when used, the technical specification of the scanning sequences should be optimized for the evaluation of the type and site of disease and lesions must be measured in the same anatomic plane by use of the same imaging examinations. Whenever possible, the same scanner should be used [Eisenhauer EA 2009].

X-ray: In general, X-ray should not be used for target lesion measurements owing to poor lesion definition. Lesions on chest X-ray may be considered measurable if they are at least 20 mm and clearly defined and surrounded by aerated lung; however chest CT is preferred over chest X-ray [Eisenhauer EA 2009].

Brain Scan: Contrast enhanced MRI is preferable to contrast enhanced CT for assessment of brain lesion(s).

Bone Scan (typically bone scintigraphy): If a bone scan is performed and a new lesion(s) is equivocal, then correlative imaging (i.e., X-ray, CT, or MRI) is required to demonstrate malignant characteristics of the lesion(s).

Note: Positron emission tomography (PET; FDG or fluoride) may be used in lieu of a standard bone scan providing coverage allows interrogation of all likely sites of bone disease and PET is performed at all assessments.

7.2.2.2 Follow-up Assessments for Subjects Permanently Discontinued from both Study Treatments

Refer to Section 4.2.1 Permanent Discontinuation from Study Treatment and Time and Events Schedule (Table 20) for follow-up assessment of subjects who are to be followed up for disease progression and/or survival after permanently discontinue from study treatment.

All subjects who permanently discontinue both study treatments without disease progression will have radiographic disease assessments performed on the same assessment schedule noted in the Time and Events Table (Table 20) until disease progression, death, starting of another anti-cancer treatment(including radiotherapy), or withdrawal of consent, whichever is documented first.

In addition, all subjects who permanently discontinue both study treatments will be followed for survival and new anti-cancer therapy according to the Time and Events Table (Table 20). Follow-up contact to assess survival and new anti-cancer therapy may be made via clinic visit, phone, or email; follow-up will continue until study completion/withdrawal/lost to follow-up or death, whichever occurs first.

7.2.2.3 Assessment at Subject Completion

If the last radiographic assessment was more than 8 weeks prior to study withdrawal and progressive disease had not been documented, a disease assessment should be obtained at the time of withdrawal.

7.2.3 Guidelines for Evaluation of Disease

7.2.3.1 Measurable and Non-measurable Definitions

Measurable lesion(s):

A non-nodal lesion that can be accurately measured in at least one dimension (the longest dimension) of:

- ≥ 10 mm with MRI or CT when the scan slice thickness is ≤ 5 mm. If the slice thickness is >5 mm, the minimum size of a measurable lesion must be at least double the slice thickness (e.g., if the slice thickness is 10 mm, a measurable lesion must be ≥ 20 mm).
- ≥ 10 mm caliper/ruler measurement by clinical exam or medical photography.
- ≥ 20 mm by chest x-ray.

Additionally, lymph nodes can be considered pathologically enlarged and measurable if:

- The short axis measures ≥ 15 mm when assessed by CT or MRI (the slice thickness is recommended to be ≤ 5 mm). At baseline and follow-up, only the short axis will be measured [[Eisenhauer EA 2009](#)].

Non-measurable lesion(s):

All lesions other than those considered measurable, including lesions too small to be considered measurable (i.e., longest diameter < 10 mm or pathological lymph nodes with a short axis of ≥ 10 mm but < 15 mm) as well as truly non-measurable lesions, which include: leptomeningeal disease, ascites, pleural or pericardial effusions, inflammatory breast disease, lymphangitic involvement of the skin or lung, and abdominal masses/abdominal organomegaly identified by physical examination that is not measurable by reproducible imaging techniques [[Eisenhauer EA 2009](#)].

Measurable disease:

The presence of at least one measurable lesion. Palpable lesions that are not measurable by radiologic or photographic evaluations may not be used as the only measurable lesion.

Non-measurable only disease:

The presence of only non-measurable lesions. **Note:** Non-measurable only disease is not allowed per protocol.

7.2.4 Response Criteria

7.2.4.1 Evaluation of Target Lesions

Definitions for assessment of response for target lesion(s) are as follows:

- Complete Response (CR): Disappearance of all target lesions. Any pathological lymph nodes must have a short axis of < 10 mm.
- Partial Response (PR): At least a 30% decrease in the sum of the diameters of target lesions, taking as a reference, the baseline sum of the diameters (i.e., percent change from baseline).

- Stable Disease (SD): Neither sufficient shrinkage to qualify for PR nor sufficient increase to qualify for progressive disease (PD).
- Progressive Disease (PD): At least a 20% increase in the sum of the diameters of target lesions, taking as a reference, the smallest sum of diameters recorded since the treatment started (i.e., percent change from nadir, where nadir is defined as the smallest sum of diameters recorded since treatment start). In addition, the sum must have an absolute increase from nadir of >5 mm.
- Not Evaluable (NE): Cannot be classified by one of the 5 preceding definitions.

Note:

- If lymph nodes are documented as target lesions the short axis is added into the sum of the diameters (i.e., sum of diameters is the sum of the longest diameters for non-nodal lesions and the short axis for nodal lesions). When lymph nodes decrease to non-pathological size (short axis < 10 mm), they should still have a measurement reported in order not to overstate progression.
- If at a given assessment time point all target lesions identified at baseline are not assessed, the sum of the diameters cannot be calculated for purposes of assessing CR, PR, or SD, or for use as the nadir for future assessments. The sum of the diameters of the assessed lesions and the percent change from nadir should, nevertheless, be calculated to ensure that PD has not been documented. If an assessment of PD cannot be made, the response assessment should be NE.
- All lesions (nodal and non-nodal) should have their measurements recorded even when very small (e.g., 2 mm). If lesions are present but too small to measure, 5 mm should be recorded and should contribute to the sum of the diameters, unless it is likely that the lesion has disappeared in which case 0 mm should be reported.
- If a lesion disappears and reappears at a subsequent time point it should continue to be measured. The response at the time when the lesion reappears will depend upon the status of the other lesions. For example, if the disease had reached a CR status then PD would be documented at the time of reappearance; if the response status was PR or SD, the diameter of the reappearing lesion should be added to the remaining diameters and response determined based on percent change from baseline and percent change from nadir.

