17. A 4-week supply of study medication should be dispensed at each scheduled study visit as of Day 1; Dosing instructions must be provided. Subjects should start treatment as soon as possible after enrolment but no later than 72 hours post-enrolment.
18. Subjects should be instructed to return study drug at each visit; compliance will be assessed by querying the subject and counting tablets/capsules. Dose modifications and interruptions must be recorded.
19. Analysis of clinical chemistry and hematology samples will be performed by a central laboratory
20. Serum pregnancy test is required at Screening. Subsequent tests may be urine tests, and should be performed as clinically indicated.
21. Blood samples for PK analysis will be drawn on Day 15 at predose (within 30 minutes prior to dosing) and 1, 2, 4, 6, and 8 hours after dosing. For subjects in China, PK blood samples will be drawn on Day 1 at predose (within 30 minutes prior to dosing) and 0.5, 1, 1.5, 2, 3, 4, 6, 8, 10 and 24 (pre dose on Day 2) hours and on Day 15 at predose (within 30 minutes prior to dosing) and 0.5, 1, 1.5, 2, 3, 4, 6, 8, 10 and 24 (pre dose on Day 16) hours after dosing. Refer to section 7.5 and 5.9.1.1 for details on pharmacokinetics blood sampling including liver PK sampling.
22. [REDACTED]

- 
25. Follow-up contact will include clinic visits, telephone contacts, and e-mail communications. The date of contact must be recorded. After treatment discontinuation, subjects should be contacted for follow-up every 12 weeks \pm 7 days until death.
 26. After treatment discontinuation, any new anti-cancer therapy initiated will be recorded until study completion/withdrawal/lost to follow-up, or death.
 27. The treatment discontinuation visit should be performed within 30 days of the subject's last dose. If a subject discontinues study treatment at a scheduled visit, the assessments performed at that visit can be used to fulfil the treatment discontinuation visit requirements. Laboratory assessments and other required assessments do not need to be repeated at the discontinuation visit if they were performed within 14 and 30 days, respectively, of the discontinuation visit. If the last disease assessment was >8 weeks prior to study withdrawal and disease progression had not been documented, a disease assessment should be obtained.

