9.3.5.1.2 Secondary Efficacy Analyses

Progression-Free Survival(PFS)

PFS will be defined as the time from first dose until the first date of either objective disease progression or death due to any cause. The date of objective disease progression will be defined as the earliest date of radiological or photographic disease progression as assessed by the investigator using RECIST, version 1.1. For subjects who have not progressed or died at the time of the PFS analysis, censoring will be performed using the date of the last adequate disease assessment or first dose for subjects without any adequate post baseline assessments. In addition, subjects with an extended loss to follow-up or who start new anti-cancer therapy prior to a PFS event will be censored at the date of the last adequate disease assessment prior to the extended loss to follow-up or start of new anti-cancer therapy, respectively. Progression free survival will be summarized descriptively using Kaplan-Meier medians and quartiles. Further details on censoring rules will be outlined in the SAP.

Overall Survival (OS)

OS is defined as the time from first dose until death due to any cause. For subjects who have not died, time to death will be censored at the last date of known contact

OS will utilize all -cause mortality and censoring will be performed using the date of last known contact for those who are alive at the time of analysis. OS will be summarized descriptively using Kaplan-Meier medians and quartiles.

Duration of Response

If data permits (i.e. a sufficient number of subjects with confirmed CR or PR), duration of response will be summarized descriptively using Kaplan-Meier medians and quartiles . Duration of Response for the subset of subjects with a confirmed CR or PR is defined as the time from first documented evidence of CR or PR until first documented disease progression or death due to any cause. Censoring rules for duration of response will follow the rules for PFS and will be outlined in detail in the SAP.

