2.1.3.5 Baseline

Baseline will be defined as the most recent non-missing value prior to the first dose of study treatment. For laboratory data, baseline will be defined as the most recent non-missing value from a laboratory prior to the first dose of study treatment.

If subjects have no value as defined above, the baseline results will be considered missing.

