5.4 Statistical models

5.4.1 Primary endpoint analysis

Overall response rate

Responses will be summarized in terms of percentage rates with 95% CIs. An exact binomial confidence interval (implemented using SAS procedure FREQ with EXACT statement) will be calculated [Clopper and Pearson 1934]

SAS procedure FREQ will be used to estimate the proportion of responders (binary outcome = 1 or “Yes”), along with the associated 95% ($=100 \times (1 - \text{two-sided } \alpha \text{ level})$) two-sided Pearson-Clopper CI.

Overall response will be determined using only target, non-target, and new lesions, using the criteria specified in the protocol.

Table 5-3 Evaluation of Overall Response for Subjects

Target Lesions	Non-Target Lesions	New Lesions	Overall Response
CR	CR or NA	No	CR
CR	Non-CR/Non-PD or NE	No	PR
PR	Non-PD or NA or NE	No	PR
SD	Non-PD or NA or NE	No	SD
NE	Non-PD or NA or NE	No	NE
PD	Any	Yes or No	PD
Any	PD	Yes or No	PD
Any	Any	Yes	PD

CR=complete response, PR = partial response, SD=stable disease, PD=progressive disease, NA= Not applicable, and NE=Not Evaluable

Evaluation of Best Overall Response

The best overall response is the best response recorded from the start of the treatment until disease progression, death, or withdrawal of consent, whichever occurs first. Best overall response will be determined programmatically based on the investigator’s assessment of response at each time point.

- To be assigned a status of SD, follow-up disease assessment must have met the SD criteria at least once after enrollment for a minimum of 49 days.
- If the minimum time for SD is not met, best response will depend on the subsequent assessments. For example, if an assessment of PD follows the assessment of SD and SD does not meet the minimum time requirement, the best response will be PD. Alternatively, subjects lost to follow-up after an SD assessment not meeting the minimum time criteria will be considered NE.

Confirmation Criteria:

- To be assigned a status of PR or CR, a confirmatory disease assessment should be performed no less than 4 weeks (28 days) after the criteria for response are first met.
- Confirmed best overall response will be determined programmatically based on RECIST 1.1.

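### The PD reference (nadir) as written omits the pre-dose baseline sum, so target-lesion PD has no reference at Week 8 and can be dated late or missed

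*Protocol*

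**What the plan says.** Protocol 7.2.4.1 uses two reference points for target lesions. Partial response is a fall of at least 30%, "taking as a reference, the baseline sum of the diameters". PD is a rise of at least 20%, and of more than 5 mm, over the nadir, where "nadir is defined as the smallest sum of diameters recorded since treatment start". The same bullet states the since-treatment-start reference twice and does not mention the baseline sum.

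The timing rules place the baseline sum before treatment:

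- Protocol 7.1.2 says baseline lesion assessments "must be performed within 4 weeks prior to enrolment".
- Protocol Table 20, footnote 17: "Subjects should start treatment as soon as possible after enrolment but no later than 72 hours post-enrolment".
- SAP 2.1.3.5: "Baseline will be defined as the most recent non-missing value prior to the first dose of study treatment".
- Table 20 puts the first post-baseline lesion assessment at Week 8, within 7 days either way.

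The SAP gives no nadir definition. SAP 5.4.1 says: "Overall response will be determined using only target, non-target, and new lesions, using the criteria specified in the protocol". It also says that confirmed best response is derived by program on RECIST 1.1. Protocol 7.2.4.5 and SAP 5.4.1 derive best response from the investigator's time-point calls and count only responses up to progression.

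**The concern.** If the PD reference is restricted to on-treatment sums, there is no earlier sum at Week 8 and target-lesion PD cannot be called there. In a subject who has already grown by Week 8, the larger Week 8 sum becomes the reference, so later growth is understated.

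Three outputs could change:

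- **PFS.** The event is dated at a later scan. If new anti-cancer therapy starts first, the outcome table in SAP 2.7.3 turns the event into a censoring.
- **Best response.** A subject could be recorded as SD instead of PD.
- **ORR and DOR membership.** Because best response closes at PD, a subject who rises at Week 8 and then shrinks is a responder under one reading and a non-responder under the other.

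**Working it through.** The plan gives no figure tied to the nadir rule, so there is nothing to reproduce. The check applies the 7.2.4.1 thresholds to invented sums, with the baseline sum left out of the nadir and then included.

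Rules: PR if the sum is at most 0.70 × baseline; PD if the sum is at least 1.20 × nadir and more than 5 mm above it; best response closes at PD; PR is confirmed at the next scan.

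| Sums in mm (baseline, then Weeks 8, 16, …) | As written | Baseline included |
|---|---|---|
| A: 50, 62, 70, 80 | Week 16: 70/62 = +12.9%, SD. Week 24: 80/62 = +29.0%, PD. Best response SD | Week 8: 62/50 = +24%, +12 mm, PD. Best response PD |
| B: 50, 57, 64, 72 | Week 16: 64/57 = +12.3%, SD. Week 24: 72/57 = +26.3%, PD | Week 8: +14%, SD. Week 16: 64/50 = +28%, +14 mm, PD |
| C: 50, 62, 34, 33, 33 | Week 16: 34/50 = −32%, PR, confirmed at Week 24. Responder | Week 8: +24%, +12 mm, PD. Non-responder |
| D: 50, 30, 28, 36 | PR, PR, then 36/28 = +28.6%, +8 mm, PD | Same |

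A fifth case, 50, 65, 77, gives (65−50)/50 = +30% and (77−50)/50 = +54% from baseline, but (77−65)/65 = +18.5% from Week 8. That is below 20%, so as written there is no PD at Week 16.

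With constant growth r per 8-week interval, PD falls at the first scan k with (1+r)^k ≥ 1.2 if baseline is included, and at scan k+1 as written. For r = 10%, 1.1² = 1.21, so Week 16 becomes Week 24. For r = 30%, Week 8 becomes Week 16.

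Case D shows why the DOR end date does not move for a subject who responds without an earlier rise. At PR the sum is at most 70% of baseline, so the on-treatment minimum is already the smaller value.

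**Possible effect on ORR** (exact two-sided 95% intervals, n = 65). One reclassified subject is 1/65 = 1.5 percentage points. A lower limit above the 25% benchmark needs 24/65 (36.9%, lower limit 25.3%); 23/65 gives 23.9%. The observed ORR is not in the documents, so starting values are assumed, at about 50% and at the 64% and 76% that Protocol 1.2.3 cites for the combination. Losing three responders gives:

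- 32/65 to 29/65: lower limit 36.6% to 32.3%.
- 42/65 to 39/65: lower limit 51.8% to 47.1%.
- 49/65 to 46/65: lower limit 63.1% to 58.2%.

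All stay above 25%.

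**The case against.** The best defence is that this is loose drafting and not a competing rule. Read literally, the protocol is barely workable, since SD also needs a reference on the growth side at Week 8. RECIST 1.1 is named as the standard: "Disease progression and response evaluations will be determined according to the definitions established in RECIST, version 1.1". For PFS the event is "disease progression as assessed by the investigator using RECIST, version 1.1". SAP 2.7.1 says the same, and SAP 5.4.1 ties confirmed best response to RECIST 1.1. The SAP sentence deferring to the protocol introduces a table that combines lesion statuses already assigned; it computes no percentage change. Baseline is also treated as essential: SAP 2.5.3 makes responses unknown without it, and SAP 2.7.3 censors PFS at first dose.

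Most of this stands. It makes actual misclassification unlikely, and it means that a sentence in the SAP alone would change no output. It does not remove the gap. Making baseline a precondition is not the same as making it the PD reference. The protocol's rule on reappearing lesions lists change from baseline and change from nadir as separate quantities. No passage states a nadir that includes baseline.

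A reader might also infer that ORR and DOR are untouched because PR is measured from baseline. Case C shows otherwise, since best response closes at PD.

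**Conclusion.** The point holds as a minor defect. The stated PD rule omits the baseline sum and gives late or missed target-lesion PD after early growth. Exposure is mainly PFS timing and SD versus PD, with a small possible effect on ORR and DOR membership. PD by new or non-target lesions can still be called at Week 8, and PFS is descriptive with no hypothesis test (SAP 2.7.2).

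Two stronger readings are not supported. A reader might infer that recorded progression dates are wrong, or that the ORR conclusion against 25% is in doubt. The documents contain no lesion data, they cite RECIST 1.1 as governing, and the margins above assume an ORR of roughly 50% or more. A reader might also try to derive a count of affected subjects, or a shift in median PFS, from the 0% first-assessment PD that Protocol 1.2.3 reports for the combination arm of an earlier study. That figure does not separate target-lesion PD from other PD and says nothing about growth below 20% at Week 8. It also comes from another population: this trial enrols subjects of East Asian origin and admits acral melanoma and prior systemic therapy. The number affected is therefore left unstated, and no PFS median shift is given.

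**What to change.** In SAP 5.4.1, define the nadir as the smallest sum of diameters on study including the baseline sum, and say that this replaces the Protocol 7.2.4.1 wording for analysis. SAP 2.1.1 gives the last patient's last visit as 19-Apr-2021, so a protocol amendment would change no assessment.

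The check carries the remedy, because the time-point calls are the investigator's. Pre-specify a programmed comparison of recorded target-lesion sums with those calls under the corrected rule, within the SAP 2.1.1 cut-off of 30-Jun-2019 for Mainland Chinese patients. Report PFS, best response, ORR and DOR re-derived under that rule as a pre-specified sensitivity analysis, and state the number of discrepant subjects even if it is zero, so that reporting does not depend on what is found. Keep the investigator-call analysis as the main one.

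The cost is one SAP sentence and a little programming on data already collected. PFS or ORR in the sensitivity analysis may be slightly less favourable.
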